2.2 SECONDARY OBJECTIVES

- To evaluate tumor response according to the IMWG criteria (Appendix 5).
- To assess duration of response (DR) and overall survival (OS).
- To assess efficacy in patients who undergo crossover from dexamethasone alone to plitidepsin and dexamethasone combination.
- To characterize and compare the safety profile on both arms in this population.
- To characterize the PK and pharmacokinetic/pharmacodynamic (PK/PD) relationship.

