3 OVERALL STUDY DESIGN

This is a prospective, open-label, two-arm, 2:1 randomized phase III study. The efficacy of plitidepsin in combination with dexamethasone (Arm A) vs. dexamethasone alone

(Arm B) will be studied by means of PFS calculated using the IMWG uniform response criteria (Appendix 5), and the evaluation of secondary efficacy endpoints.

Patients in the control arm (dexamethasone alone, Arm B) who have documented disease progression according to the Investigator's criteria after a minimum of eight weeks from randomization should be offered crossover to combination arm (plitidepsin + dexamethasone, Arm A) upon Sponsor agreement.

An Independent Review Committee (IRC), consisting of medical specialists directly involved in the care of MM patients, but not being investigators or subinvestigators in this trial, will review all efficacy data and will assign the date of progression/censoring and objective response according to their independent evaluation. This IRC will be blinded to treatment arm allocation and identity of the cases reviewed (Section 5.6).

An Independent Data Monitoring Committee (IDMC), including specialists in MM and in medical statistics, will review the results of the analysis performed by an independent statistician. Then, the IDMC will advise the Sponsor about the study conduct.

Operational details for the above mentioned IRC and IDMC will be detailed in the corresponding charters.

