8 STUDY EVALUATIONS

8.1 EFFICACY

Primary

• PFS, according to IRC assessment, as per intention-to-treat (ITT) analysis.

Secondary

- Objective RR.
- Best overall response including rate of minor response (MR) or better (according to the IMWG criteria) (Appendix 5).
- RR to combination treatment in patients who crossed over after progression on dexamethasone alone.
- Time-to-event endpoints: DR and OS.
- Intrapatient response and PFS comparison of patients who crossed over from dexamethasone alone (Arm B) to plitidepsin plus dexamethasone combination (Arm A).

The primary study analysis will be based on externally assessed PFS data in the **ITT** efficacy population, defined as *all patients randomized to either treatment arm*.

PFS will be calculated from randomization to the first evidence of PD (IMWG criteria) or death due to any cause. If the patient receives further antitumor therapy before PD and within the timeframe expected for first follow-up, PFS will be censored on the date of the last disease assessment prior to the administration of this antitumor therapy. If the patient is lost to follow-up for the assessment of progression, or has more than one missing follow-up between the date of last tumor assessment and the date of progression, death or further antitumor therapy, the PFS will be censored at the date of last valid tumor assessment before the missing evaluations.

DR will be calculated from the date of first documentation of response to the date of disease progression or death. The same censoring rules described above for PFS calculation will be also considered for DR.

OS is defined as the time from the date of randomization to the date of death or last contact.

An external IRC, blinded to treatment arm, will assign a progression or censoring date for each patient based on laboratory data and radiologic and bone marrow assessments when required and evaluation of all relevant clinical information, according to a predefined algorithm provided in a separate charter. Both IRC and Investigator's assessment will be used for the determination of RR, DR and PFS.

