10 STATISTICAL METHODS

10.1 SAMPLE SIZE

- 1. Arm A (plitidepsin plus dexamethasone combination): approximately 167 patients.
- 2. Arm B (dexamethasone single agent): approximately 83 patients.

The number of patients randomized in the trial has been calculated based on PFS estimates obtained from the previous phase II study (APL-B-014-03).

Approximately 210 progression or death events would be needed in this trial to detect a HR of 0.625 in favor of the combination arm (equivalent to an increase of 60% in PFS, i.e., from 10 to 16 weeks, from 12 to 19.2 weeks, from 16 to 25.6 weeks, etc.) with 90% power and 1-sided 2.5% significance level. As a preliminary hypothesis, it is estimated that up to 250 randomized patients will be needed to achieve the 210 events in 24-30 months.

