4.1 Analysis sets definitions

“All Randomized Patients” analysis set is defined as all patients who are randomized to either treatment arm, independent of whether they received the study drug.

“All Treated Patients” analysis set is defined as all randomized patients who receive at least part of one dose or infusion of the investigational agents.

“All Evaluable Patients” analysis set is defined as all randomized patients who have completed at least one full cycle of treatment or have received two incomplete cycles followed by at least one response assessment not less than eight weeks (\pm one week) after treatment onset. Patients withdrawn from the study due to early disease progression or treatment-related toxicity will be considered as “early progression” or “treatment failure”, respectively, even though they have not received a full cycle. Patients withdrawn due to significant clinical deterioration of unknown reason, hypersensitivity reactions, or refusal to continue on study for any reason or unrelated AEs without any disease assessments after the start of study treatment or those patients with a protocol deviation resulting in an impossibility of drawing conclusions about the efficacy of the study therapy will be considered not evaluable for efficacy and their response will be categorized as “non evaluable”.

“All Responder Patients” analysis set is defined as all evaluable patients who have minor response or better as overall best response.

“All Crossover Patients” analysis set is defined as all patients randomized to Arm B who have documented disease progression after their eighth week from randomization and cross over to Arm A.

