6 STATISTICAL METHODOLOGY FOR EFFICACY

6.1 *Planned analyses and definitions*

Protocol-specified analyses are foreseen at the time of the futility evaluation (approximately 40 patients in Arm A), final PFS analysis (main endpoint, approximately 210 progression or death events) and follow-up evaluation of OS at 24 months after the inclusion of the last patient or 80% of death events (approximately 200 death events), whichever occurs first. Accrual will be on-hold while data for the futility analysis is being assessed, when 40 patients in Arm A fully evaluable for response have been accrued.

6.1.1 *Early futility analyses*

An early futility analysis will be performed when information from the first 40 patients in Arm A are evaluable for response. A response rate (IMWG criteria) of at least 30% (12 or more responses by IRC review) will be taken as threshold for continuation of the study. A minimum response rate of 30% has been considered as clinically significant in this setting. This result will ensure that the lower limit of the exact binomial 95% Confidence Interval for the response rate will be greater than 15% (95% CI in case of 12 responses would be 16.6% - 46.5%).

However, the efficacy and safety information from all randomized patients in both arms at that time will be used by the IDMC to provide the sponsor with a recommendation for the further study conduct. No claim for superiority in efficacy will be formulated in this interim analysis and no alpha-spending for the analysis of PFS is foreseen.

6.1.2 *Final analyses*

Primary endpoint.

Efficacy will be assessed by comparing the PFS in each treatment arm.

Progression-free survival (PFS) is defined as the time from the date of randomization to the date of documented progressive disease (PD) by IMWG criteria or death (regardless of the cause of death). If the patient receives further antitumor therapy before PD, PFS will be censored on the date of the last disease assessment prior to the administration of this antitumor therapy. If the patient is lost to follow-up for the assessment of progression, or has more than one missing follow-up between the date of last tumor assessment and the date of progression, death or further antitumor therapy, the PFS will be censored at the date of last valid tumor assessment before the missing evaluations.

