An external review committee blinded to treatment arm will assign the objective response and a progression or censoring date for each patient based on laboratory data, radiologic and bone marrow assessments when required and evaluation of all relevant clinical information; then, this information will be merged with the date of death from the death report forms and with further antitumor therapy data for the calculation of PFS. Patients with missing IRC evaluations will have their PFS censored at randomization date.

The primary study analysis will be based on externally assessed PFS data in the “All Randomized Patients” population, defined as all patients randomized to either treatment arm.

By design, disease response will be assessed every four weeks symmetrically across treatment arms irrespectively of treatment delays or omissions. Disease assessments (e.g., serum or urine M-spike, sFLC) and evaluation of extent of disease will be done within two weeks before randomization and every four weeks thereafter in the absence of PD while on treatment. If disease progression has not occurred at treatment termination, then disease assessments should continue every four weeks until evidence of disease progression or other antitumor therapy, whichever occurs first, and then will be followed every three months for survival until death, or until the date of study termination, whichever occurs first.

Study termination date is defined as the date in which 80% of death events occurred, 24 months after the accrual of the last randomized patient, or IDMC recommendation (whichever occurs first).

PFS and objective tumor response will be assessed according to IMWG criteria. Centralized laboratory reports and copies of computed tomography scans (CT-scans), magnetic resonance imaging (MRI) (in case of soft tissue plasmacytoma) and any other documented means to evaluate tumor response or progression should be available for IRC review.

For patients within the “All Crossover Patients” dataset, the PFS is defined as the time from the day of the last disease assessment, before the first administration of the combination, to the date of documented progressive disease (PD) by IMWG criteria or death (regardless of the cause of death). The same censoring rules described above for PFS calculation will be considered.

Secondary endpoints.

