11.3.4.5 Analysis of crossover

Table 11.3.4.5.1 RR to combination treatment in patients who crossed over from Arm B to Arm A (“All Crossover Patients” population)

		After crossover (N,%)							
		sCR	CR	VGPR	PR	MR	SD	PD	NE
Before crossover	sCR								
	CR								
	VGPR								
	PR								
	MR								
	SD								
	PD								
	NE								

Table 11.3.4.5.2 Inpatient PFS comparison of patients who crossed over from Arm B to Arm A (“All Crossover Patients” population)

PFS	Before crossover	After crossover
Median		
PFS at 6 months		

Table 11.3.4.5.3 PFS comparison of patients (“All Randomized Patients” population)

PFS	Arm A	Arm B	
		Before crossover	After crossover
Median			
PFS at 6 months			

Listing 11.3.4.5.4 Best response and PFS before and after crossover.

Patient id.	Cycle of crossover	Best response		PFS	
		Before crossover	After crossover	Before crossover	After crossover
...					

Listing 11.3.4.5.5 Best response and PFS before in crossover patients.

Patient id.	Independent review assessment				Investigator assessment			
	Best response	PFS	PFS event	PD confirmation	Best response	PFS	PFS event	PD confirmation
...								

Table 11.3.4.5.6 Time to crossover

	N	Median	Min	Max
Time to crossover (months)				

Table 11.3.4.5.7 Baseline characteristics comparison patients without crossover vs crossover

Variable**	Value	N	Without Crossover	Crossover	p-value*
Sex	F	XXX	XX (XX.X%)	XX (XX.X%)	X.XXXX
	M	XXX	XX (XX.X%)	XX (XX.X%)	
Age	Median(range)	XXX	XX.X (XX-XX)	XX.X (XX-XX)	X.XXXX
...					

(*)Fisher's exact test (categorical variables); Mann-Whitney-Wilcoxon (continuous variables)

(**)Sex, age, PS (ECOG), BSA, Durie Salmon stage, International Staging System, Secretary/Non-secretory, MM type, time from diagnosis, time from last PD, number of prior lines, status to prior therapy, status to prior bortezomib therapy, status to prior thalidomide/lenalidomide therapy, status to prior IMiD therapy, status to prior PIs therapy, stem cell transplantation, plasma cells, hemoglobin, creatinine, calcium, genetic risk, lytic lesions and plasmacytomas.

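### The before/after-crossover PFS comparison is biased, mostly against crossover: only the before period carries a week-8 condition, and the after period starts before the first combination dose

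*SAP*

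**What the plan says.** - **Eligibility.** Protocol section 3 says that control patients with documented "disease progression according to the Investigator's criteria after a minimum of eight weeks from randomization should be offered crossover" to the combination, subject to sponsor agreement.
- **Analysis set.** SAP 4.1 defines the crossover set as "all patients randomized to Arm B who have documented disease progression after their eighth week from randomization and cross over to Arm A".
- **Clock before crossover.** The general PFS definition in SAP 6.1.2 applies: "time from the date of randomization to the date of documented progressive disease (PD) by IMWG criteria or death".
- **Clock after crossover.** For this set, SAP 6.1.2 says "the PFS is defined as the time from the day of the last disease assessment, before the first administration of the combination". For response, the reference is the protein value taken immediately before the combination.
- **Display.** SAP Table 11.3.4.5.2, "Inpatient PFS comparison of patients who crossed over from Arm B to Arm A", puts the median and 6-month PFS before and after in adjacent columns. Table 11.3.4.5.3 adds Arm A. Neither names the assessor or carries a caveat.
- **Status.** SAP 4.2 and 6.2.3 and Protocol 10.2.3.5 call the comparison exploratory. Protocol 8.1 lists it among the secondary evaluations, and Protocol 2.2 has as a secondary objective "To assess efficacy in patients who undergo crossover from dexamethasone alone to plitidepsin and dexamethasone combination".

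**The concern.** The two columns are not alike. A patient contributes a before-crossover time only if that time reached about 8 weeks. Faster progressors are left out because of their outcome, which lengthens the before column. After crossover the same patients may progress at any time.

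The after-crossover clock has the opposite fault. Any interval between the last assessment and the first combination dose is credited to the combination, although the patient is not yet receiving it and must be alive to be dosed.

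What is at stake is how a stated secondary objective is read. Someone looking at Table 11.3.4.5.2 would take similar medians to mean that adding plitidepsin after progression achieved nothing. The plan's own assumptions do not support that reading.

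**Working it through.** The plan gives no figure for this comparison. Its PFS event calculation supplies the control medians, so I checked that first.

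**1. The plan's own figure.** Inputs (SAP 5.2, Protocol 10.1): HR 0.625, 90% power, one-sided 2.5%, 2:1 allocation. Schoenfeld: (1.960 + 1.282)² / [(2/3)(1/3)(ln 0.625)²] = 10.51 / (0.2222 × 0.2209) = 214.1, rounded up to 215, against 210 stated. Power at 210 events is 89.4%. The stated medians, "equivalent to an increase of 60% in PFS, i.e., from 10 to 16 weeks, from 12 to 19.2 weeks, from 16 to 25.6 weeks, etc", each give HR 0.625. I use control medians m of 10, 12 and 16 weeks.

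**2. Does progression at the week-8 visit qualify?** Protein assessments fall on Day 1 of each 4-week cycle (Protocol 5.11), and randomization is 0 to 7 days before the first dose (SAP 5.1). Cycle 3 Day 1 is thus nominally 2 × 28 = 56 to 63 days after randomization. Under the protocol's minimum of eight weeks it probably qualifies. SAP 4.1 can be read as requiring a later visit. I carry both readings.

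**3. Share of Arm B excluded.** Assume exponential PFS, so P(progression by t) = 1 − 2^(−t/m).
- Week-8 progression qualifies (only the week-4 visit is lost): 1 − 2^(−4/m) = 24%, 21%, 16%.
- Progression must come later: 1 − 2^(−8/m) = 43%, 37%, 29%.

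**4. Within-patient comparison, m = 12, visits every 4 weeks, no gap before the first combination dose.** The chance of passing one visit interval is q = 2^(−4/12) = 0.7937 before crossover. After crossover it is r = q with no effect, or r = 2^(−4 × 0.625/12) = 0.8655 at the target. Let s be the first qualifying visit (2 = week 8, 3 = week 12).
- P(after longer) = r^(s−1) × (1−q)r/(1−qr)
- P(tie) = r^(s−1) × (1−q)(1−r)/(1−qr)
- No effect: the fractions are 0.2063 × 0.7937/0.3700 = 0.4425 and 0.2063²/0.3700 = 0.1150.
- Target effect: they are 0.2063 × 0.8655/0.3130 = 0.570 and 0.2063 × 0.1345/0.3130 = 0.089.

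| | Better after | Tie | Worse after |
|---|---|---|---|
| No effect, week 8 qualifies | 35% | 9% | 56% |
| No effect, later only | 28% | 7% | 65% |
| Target, week 8 qualifies | 49% | 8% | 43% |
| Target, later only | 43% | 7% | 51% |

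**5. Medians, ignoring visit rounding and conditioning exactly at week 8.** The before median is 8 + m = 18, 20, 24 weeks. The after median is m with no effect, or 1.6m = 16, 19.2, 25.6 at the target. After/before is 0.56, 0.60, 0.67 with no effect (unbiased value 1.0) and 0.89, 0.96, 1.07 at the target (unbiased value 1.6).

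**6. The early start.** The documents do not state the gap from last assessment to first combination dose, so I assume 0 to 4 weeks. A 4-week gap adds 4 to each after median. The ratios become 0.78, 0.80, 0.83 with no effect and 1.11, 1.16, 1.23 at the target. In step 4 a 4-week gap offsets one visit. With no effect this gives 44% better and 44% worse if week 8 qualifies, and 35% and 56% if not.

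**7. Consistently slow progressors.** With a shared gamma frailty of variance 0.5 (assumed), m = 12 and no gap, the share better after crossover is 31% to 36% with no effect and 45% to 49% at the target. The picture hardly changes.

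**8. Two possible remedies, m = 12.**
- The same condition on both periods: the factor r^(s−1) drops out. No effect gives 44% better and 44% worse. The target gives 57% better and 1 − 0.570 − 0.089 = 34% worse.
- Subtracting 8 weeks from the before times only, with week-8 progression qualifying: no effect gives 0.4425 + 0.1150 = 56% better and 0.7937 × 0.4425 = 35% worse. An inert drug would look beneficial.

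**The case against.** The strongest reply is that the comparison is exploratory, has no test, hazard ratio or decision rule, and affects no confirmatory result. That stands and limits the weight of the point. It does not make the display neutral, because efficacy after crossover is a secondary objective.

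The SAP also plans a baseline comparison of patients with and without crossover, their PFS (Table 11.3.4.1.14), time to crossover, and a listing with both assessors' results. These describe who crossed over. They do not correct the before/after contrast.

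The early start is the weaker limb. The protein reference taken immediately before the combination suggests a short gap, although that rule sets the response baseline and not the PFS clock. PFS before crossover also starts up to 7 days before dosing.

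A reader might infer that the crossover data cannot show benefit at all. The documents do not support that. With a gap of up to 4 weeks the net bias is against crossover or at most neutral. PFS after crossover is itself an endpoint in SAP 3.3, and the week-8 condition on the before period does not alter its measured length. Response is re-baselined and touched by neither fault.

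A reader might also infer that every before-crossover time is at least 8 weeks. That is strict only for investigator-assessed progression. An IRC date may fall earlier, and the tables do not say which is used.

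**Conclusion.** The point holds for the PFS comparison only. As written, the before/after contrast does not estimate the effect of adding plitidepsin, and it is tilted mostly against crossover. At a control median of 12 weeks an inert drug would look worse in 56% to 65% of patients. A drug with the full target effect would split them roughly evenly. A ratio near or below 1 is therefore not evidence of no benefit, while a clearly longer PFS after crossover would still point to benefit.

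The sizes rest on the planning medians, a constant hazard, 4-weekly visits and an assumed gap of 0 to 4 weeks. The documents set no limit on that gap, and a longer one could turn the net bias in favour of crossover. The 1.6 benchmark is the plan's randomized effect; no effect size is stated for crossover.

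**What to change.** In SAP 6.1.2, 6.2.3 and the tables of 11.3.4.5:
1. Start PFS after crossover on the date of the first combination dose. Keep the last protein value before it as the reference.
2. Add a comparison with the same week-8 condition on both periods, that is, among patients also progression-free to the same point after crossover. Do not subtract 8 weeks from the before times alone, for the reason in step 8 of the working.
3. Name the assessor in Tables 11.3.4.5.2 and 11.3.4.5.3. Keep the Arm A column. Table 11.3.4.5.3 is titled for all randomized patients, so state whether its Arm B before column is all of Arm B or only crossover patients; if only crossover patients, footnote the 8-week selection.
4. Label the unadjusted medians as descriptive and not evidence for or against benefit.

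The cost is SAP wording and some reprogramming, with no new data. PFS after crossover becomes slightly shorter. The matched comparison has fewer patients: at m = 12 it keeps r^(s−1) of the crossover set, 63% to 79% with no effect and 75% to 87% at the target. It leaves out early failures after crossover, so their number should be reported beside it.

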4.2 Efficacy populations

The “All Randomized Patients” analysis set will be used for the primary endpoint analysis of Progression-free survival (PFS) and the main efficacy analysis, as well as for all OS analyses.

For futility analysis based on objective response rate, the “All Evaluable Patients” analysis set will be used.

The “All Randomized Patients” and “All Evaluable Patients” datasets will be used for the final analysis of RR.

The “All Responder Patients” dataset will be used for the duration of response (DR) calculation.

[figure not shown]
The “All Crossover Patients” dataset will be used for the exploratory inpatient comparison of response and PFS (before and after crossover).

4.3 Safety population

The safety analysis is based on the “All Treated Patients” analysis set.

5 SAMPLE CONSIDERATIONS

5.1 Randomization

Patients fulfilling all eligibility criteria will be stratified according to the Eastern Cooperative Oncology Group (ECOG) Performance Status (PS) score (0 and 1 vs. 2) and Durie-Salmon stage at diagnosis (I/II vs. III) and then randomized using a 2:1 randomization procedure to Arm A (plitidepsin in combination with dexamethasone) or Arm B (dexamethasone alone). Randomization will be used to avoid bias in the assignment of patients to treatment, and to increase the likelihood that known and unknown patient attributes (e.g., demographics and baseline characteristics) are evenly balanced across treatment groups.

Randomization of patients should occur as close in time as possible before administration of the first dose of study drug(s) and must occur within 7 days of the patient receiving the first dose of study treatment. The randomization number and treatment code will be assigned after phoning into the Interactive Voice Response System (IVRS).

On the basis of the patient identification and stratum information, the IVRS will assign a treatment code, which will dictate the treatment assignment for that patient.

Patients will be assigned to each group by strata random list, so that a patient will have a two-thirds chance of getting Arm A (plitidepsin in combination with dexamethasone) and a one-third chance of getting Arm B (dexamethasone alone). The random permuted blocks method will be used; the size of the blocks in the randomization list will be fixed and not accessible to investigators. To select the blocks, a uniform (0, 1) variable with a random seed will be used.

5.2 *Sample size*

The number of patients randomized in the trial has been calculated based on PFS estimates obtained from the previous phase II study (APL-B-014-03).

1. **Arm A** (plitidepsin plus dexamethasone combination): approximately 167 patients.
2. **Arm B** (dexamethasone single agent): approximately 83 patients.

Approximately 210 progression or death events would be needed in this trial to detect a HR of 0.625 in favor of the combination arm (equivalent to an increase of 60% in PFS, i.e., from 10 to 16 weeks, 12 to 19.2 weeks, 16 to 25.6 weeks) with 90% power and 1-sided 2.5% significance level. As a preliminary hypothesis, it is estimated that up to 250 randomized patients will be needed to achieve the 210 events in 24-30 months. For the calculation of the number of events needed, the target HR to be detected is 0.625, with 90% power and 2.5% unilateral significance level. This is equivalent to a minimum 60% increase in PFS, which has been considered statistically and clinically significant by the Sponsor.

An early futility analysis will be performed with the data collected when 40 patients in Arm A are evaluable for response. A response rate (IMWG criteria) of at least 30% (twelve or more responses by IRC review) will be taken as threshold for continuation of the study. A minimum response rate of 30% has been considered as clinically significant in this setting. This result will ensure that the lower limit of the exact binomial 95% Confidence Interval for the response rate will be greater than 15% (95% CI in case of 12 responses would be 16.6% - 46.5%).

However, the efficacy and safety information from all randomized patients in both arms at that time will be used by the independent data monitoring committee (IDMC) to provide the Sponsor with a recommendation for further study conduct.

The final PFS analysis will be performed when at least 210 progression or death events are observed.

An interim analysis of OS will be performed concomitantly with the final PFS analysis. In addition, a final analysis of OS will be performed when 80% of death events (approximately 200 death events) have occurred or 24 months after the inclusion of the last patient, whichever occurs first. At the interim OS analyses, the significance level determined by the O'Brien-Fleming (1) boundary with overall 2.5% 1-sided significance level will be used.

